**Funding Source:**

This project has received preliminary approval from the Merck Investigators Studies Program (MISP) with a budget of \$72,146.78. The budget for the study includes cost of the drug (Sugammadex), pharmacy and IRB fees, and payment for the research team. We will provide the budget for the study along with the rest of the protocol.

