Sugammadex has been anecdotally reported to decrease rates of postoperative urinary retention following laparoscopic inguinal hernia repair. The more rapid reversal of neuromuscular blockade helps to explain this claim. In other areas of surgery, such as orthopedics, Sugammadex has already been associated with reduced anticholinergic usage and decreased rates of postoperative urinary retention. The cost efficacy of Sugammadex has yet to be determined as it is more expensive than traditional reversal counterparts; however, if it significantly decreases rates of postoperative urinary retention it could reduce healthcare costs that are downstream. Given that the reported incidence of postoperative urinary retention is high after laparoscopic inguinal hernia repair, and given this is one of the most common general surgery operations performed, the results of this study will certainly be widely applicable.

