### **Study Objectives**

#### *Objectives –*

1. The primary objective of this study will be to compare urinary retention rates when using Sugammadex for neuromuscular reversal compared to neostigmine. The patients receiving Sugammadex will be enrolled prospectively and those who received neostigmine will be identified retrospectively on chart review.
2. We will secondarily evaluate length of stay (in postoperative recovery or in the hospital), charges accrued by patients, and quality of life compared to patients who received neostigmine.

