#### *Hypotheses –*

1. We hypothesize that the use of Sugammadex as a neuromuscular reversal agent will decrease postoperative urinary retention after laparoscopic inguinal hernia repair compared to patients who received neostigmine.
2. We also hypothesize that there will be decreased postoperative length of stay, total hospital charges accrued by patients, and no negative impact on quality of life compared to patients who received neostigmine.

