On the day of surgery, the research team will be present in the preoperative area and communicate directly with the anesthesia team that this is a patient who will be receiving Sugammadex; this communication is important because Sugammadex can only reverse vecuronium or rocuronium. The Investigational Drug Service Department at Atrium Health will be notified the day before that there will be a patient included in the study the day prior to the operation. Their pharmacists will have the drug present for the anesthesiology team. This will not be a blinded study, so the anesthesia team and even the surgeon can know that the patient is receiving Sugammadex. In this study, patients will receive Sugammadex, in accordance with FDA approved labeling, following laparoscopic inguinal hernia repair and then be retrospectively matched against a group of patients who did not receive Sugammadex.

The definition that we will be using for urinary retention is the inability to void at six hours postoperatively which will be recorded in the postoperative recovery area and the same definition for urinary retention will be applied to the comparative retrospective cohort. Patients will be required to void prior to their discharge from the hospital. The requirement for urinary catheterization will be secondarily recorded. The details of the patient's operation, postoperative recovery, and potential admission encounter will be obtained and enter into the electronic health record into our pre-existing hernia database. Details about the cost to the patient will be obtained from a monthly billing statement that is generated for our department in Epic™ Systems. Patients will be seen in clinic postoperatively, typically within one to two weeks, and a quality of life questionnaire will be administered. This questionnaire is the same form that is typically used in our surgical clinics and will provide a means for retrospective comparison.

The data entry will be performed by two data analysts that are employed by our division. Once this data has been entered for all patients, our statistician will perform an analysis using Statistical

Analysis Software, version 9.4 (SAS Institute, Inc., Cary, NC) and send this data to the investigators for review. The principal investigator (PI) and co-investigators will be responsible for composing the abstracts and manuscript for this project.

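### The grant pays for Sugammadex but charges come only from a billing statement, so the charge comparison may leave out the drug

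*Combined protocol and SAP*

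**What the plan says.** Funding Source reports "preliminary approval from the Merck Investigators Studies Program (MISP) with a budget of" $72,146.78 and states: "The budget for the study includes cost of the drug (Sugammadex), pharmacy and IRB fees, and payment for the research team". Study Design/Methods has the Investigational Drug Service notified the day before surgery: "Their pharmacists will have the drug present for the anesthesiology team".

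The same section names one source for cost: "Details about the cost to the patient will be obtained from a monthly billing statement that is generated for our department". Neither it nor Statistical Analysis and Sample Size Justification adds a Sugammadex charge to the Sugammadex arm, or removes reversal drugs from both arms.

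Background and Rationale explains why cost is of interest: "The cost efficacy of Sugammadex has yet to be determined as it is more expensive than traditional reversal counterparts". It goes on to suggest that fewer retentions could reduce later costs. Objectives lists "charges accrued by patients, and quality of life compared to patients who received neostigmine" as secondary comparisons, and Hypotheses expects "decreased postoperative length of stay, total hospital charges accrued by patients, and no negative impact on quality of life". The neostigmine patients are found by retrospective chart review, so this grant did not supply their reversal drug.

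The outcome has no single name. It is charges in Objectives and Hypotheses, cost to the patient in Study Design/Methods, and hospital cost in the statistical section.

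**The concern.** The cost question is a trade-off: a dearer reversal drug on one side, fewer retention-related charges on the other. If the grant pays for the drug and the bill is the only source, the first side may never enter the Sugammadex total. Matching cannot repair this, because the gap comes from who pays for the drug and not from patient characteristics.

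The hypothesis of lower total charges could then look better supported than it is, and the result would not carry over to a hospital that has to buy the drug.

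**Working it through.** **Inputs from the protocol.** Retention 7% against 0.5%, 140 per group, 80% power, two-sided 0.05 (Statistical Analysis and Sample Size Justification); budget $72,146.78 (Funding Source). The protocol gives no drug price, charge per retention or standard deviation of charges.

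**1. The plan's own figure.** Enumerating the two-sided Fisher test at 140 per group, 7% against 0.5%, gives 80.3% power; the pooled normal approximation gives 82.0%. The stated 80% is reproduced. It concerns retention only. No sample size or power is given for cost, and the point here does not depend on it.

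**2. What each billing possibility does to the comparison.** Let S be the Sugammadex charge per patient, N the neostigmine charge, and R the difference in all other charges (Sugammadex minus neostigmine). The full difference is (S − N) + R.

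| On the statement | Difference observed | Error |
|---|---|---|
| Both drugs | (S − N) + R | none |
| Neostigmine only | R − N | too low by S |
| Neither drug | R | too low by S − N |
| Sugammadex only | S + R | too high by N |

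The protocol does not say which row applies. The grant line and the Investigational Drug Service route make the second or third row likely. In both of those the error favours Sugammadex; in the third this uses the Background statement that Sugammadex is the more expensive drug and assumes that charges follow price.

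**3. The hurdle that is left out.** Let D = S − N. The planning difference is 0.07 − 0.005 = 0.065, so 1/0.065 = 15.4 patients are treated per retention avoided, and 140 × 0.065 = 9.1 retentions are avoided in the arm. If savings come only from avoided retentions, break-even requires a saving per avoided retention of D/0.065.

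| D per patient (assumed) | Arm total, 140 × D | Break-even saving per avoided retention |
|---|---|---|
| $50 | $7,000 | $769 |
| $100 | $14,000 | $1,538 |
| $200 | $28,000 | $3,077 |

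With neither drug on the statement, the hurdle appears to be $0. With neostigmine alone on it, Sugammadex starts ahead by N.

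**4. What the budget can say about size.** $72,146.78/140 = $515.33. This is the most the grant could spend on drug per Sugammadex patient if it paid for nothing else. It does not cap the hospital's charge for the drug, so it does not bound the omission.

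**The case against.** The strongest reply is that the central fact is not in the documents. No section says that grant-paid Sugammadex will be missing from the bill. The itemised budget and the consent form, which might settle who is billed, were not available to this review. If the hospital still posts the charge, the bias shrinks or disappears. This stands, and it is why the point is conditional.

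A reader might infer that the plan compares a total without Sugammadex against a total that includes neostigmine. The second half is not supported. The statement is generated for a surgical department, and nothing shows that it itemises anesthesia drugs in either arm.

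It can also be said that a comparison without the drug answers a legitimate question about downstream costs. The Study Summary gives need for admission as an example of the cost it expects to fall. That stands for downstream cost. It does not cover a hypothesis about total hospital charges, or a rationale that rests on the drug's higher price.

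Finally, the dollar figures rest on assumed prices and count only savings from avoided retention, whereas the protocol also expects shorter stays. A reader might infer that the omission would decide whether the charges test is significant. With no price and no standard deviation of charges, the documents cannot show that.

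**Conclusion.** The concern holds in conditional form. The grant covers Sugammadex, the billing statement is the only named source of charges, and nothing adds the drug back. Followed as written, the plan would probably leave the more expensive drug out of a comparison meant to test total charges. That omission would lower only the Sugammadex total. If neostigmine is also missing, the net error is the difference between the two charges and still favours Sugammadex, provided its charge is the higher.

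The size is unknown. What can be said is that each avoided retention must save about 15.4 times the net extra drug charge, given the planning rates and no other source of savings. It is not established that Sugammadex is off the bill, that neostigmine is on it, or that the test result would change. Only the secondary cost outcome is affected. The change is worth making because it is cheap and the outcome cannot be interpreted without it.

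**What to change.** In Study Design/Methods and in Statistical Analysis and Sample Size Justification:

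- Give the cost outcome one definition and use it throughout.
- State whether Sugammadex and neostigmine appear on the departmental billing statement.
- Count the reversal drug exactly once in both arms. Where the bill lacks it, add the hospital's standard charge for the vials or drug used, taken from dispensing or anesthesia records. Where it is already billed, add nothing; an unconditional addition could count it twice.
- Exclude research-only charges.
- Test the charges hypothesis on this total, and also report the total without reversal drugs as the downstream-cost comparison.

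The cost is one extra pharmacy data item per patient and a short protocol edit, with no new patients or procedures. The sponsor should expect a cost result less favourable to Sugammadex if the drug would otherwise have been left out.

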**Study Summary:**

Postoperative urinary retention following laparoscopic inguinal hernia repair occurs in approximately one out of ten patients. The more rapid reversal of neuromuscular blockade with Sugammadex has empirically been associated with low rates of postoperative urinary retention. In this study, patients will receive Sugammadex following laparoscopic inguinal hernia repair and then be retrospectively matched against a group of patients who did not receive Sugammadex. The primary aim of this study will be to compare the rate of postoperative urinary retention between patients receiving Sugammadex and those receiving traditional reversal agents (e.g. neostigmine which has a retention rate of 5-11%). We will also examine difference in cost and quality of life between the two groups. Our hypothesis is that the use of Sugammadex will decrease rate of postoperative urinary retention, decrease associated cost, such as need for admission, and not negatively impact quality of life.

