**Statistical Analysis and Sample Size Justification:**

*Variables/Time Points of Interest* – Basic demographic information for each patient will be obtained from the medical record, such as age, gender, ASA class, and prior medical histories/surgeries. This information will aid in propensity matching for the study. The propensity match will be 1:1 with an equal number of patients in each group. The match will ensure that there is no statistical difference in data points between the groups and it will be performed by our statistician using SAS. The primary outcome variable, postoperative urinary retention, is a categorical variable (yes/no) that will be documented in postoperative recovery after the patient's operation. Length of stay and hospital cost, continuous variables, will be recorded at the completion of the patient's hospital stay. Information about quality of life will be obtained postoperatively in clinic. The demographic information, primary and secondary outcomes will be entered into our institutional database along with the other information that is typically recorded, such as operative characteristics and patient follow up.

*Statistical Methods* - Data will be analyzed using Statistical Analysis Software, version 9.4 (SAS Institute, Inc., Cary, NC); this task will be performed by the statistician employed by our division. Descriptive statistics will be reported as means with corresponding standard deviations for continuous variables and percentages for categorical variables. Continuous and ordinal variables will be evaluated with the Wilcoxon-Mann Whitney and the Kruskal-Wallis tests. The Wilcoxon-Mann Whitney test will be used when normality exists and there are two variables for comparison, otherwise, the Kruskal-Wallis test will be used. For categorical variables, a Pearson chi-square will be used, and a Fisher exact test will be utilized with a small sample size (i.e. less than five). A two-sided p-value of <0.05 will be used for all significance determinations.

*Power/Sample Size* – Using SAS, the power for our study was calculated using the postoperative urinary retention rate at our institution, 7%, compared to a current 0.5% postoperative urinary retention rate using Sugammadex. With 80% power, we would need to enroll 140 patients per group. The data for this project will be interpreted by the PI for the project as well as the co-investigators.

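### The economic outcome is named as charges, cost to the patient and hospital cost, and its only source, a departmental billing statement, is not shown to hold the charges that retention would raise

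*Combined protocol and SAP*

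**What the plan says.** The combined protocol and SAP describes its economic outcome differently from section to section:

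- Study Summary: the drug is expected to "decrease associated cost, such as need for admission".
- Objectives, item 2: the secondary outcomes are "length of stay (in postoperative recovery or in the hospital), charges accrued by patients, and quality of life".
- Hypotheses, item 2: a decrease is expected in "total hospital charges accrued by patients".
- Study Design/Methods: "Details about the cost to the patient will be obtained from a monthly billing statement that is generated for our department". The statement comes from the Epic system.
- Statistical Analysis and Sample Size Justification: "Length of stay and hospital cost, continuous variables, will be recorded at the completion of the patient's hospital stay".

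No section defines the variable, lists the lines that the statement contains, or names another source of charges. The hernia database receives details of the operation, the recovery and any admission, but nothing says that it receives charges.

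Three other passages bear on the point. Background and Rationale lists what retention can lead to: longer time in the recovery unit, an overnight admission, an emergency department visit, a catheter and more physician assessment. It also argues that a dearer drug might pay for itself through lower downstream costs. Funding Source says that the study budget covers Sugammadex and pharmacy fees.

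**The concern.** Two gaps separate the hypothesis from the data.

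The first is what is measured. Billed charges, a patient's liability and the hospital's expenditure are three different amounts for the same stay. A billing statement can supply either of the first two. It cannot supply the third without a conversion, and none is planned. An analyst following the text could extract different figures, and a reader of the results could not tell which had been compared.

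The second is what is covered. Most of the consequences of retention that the protocol lists are facility items. The one named source is a statement produced for a department, with its contents undescribed. If it carries only part of the encounter, the comparison loses some of the pathway it is meant to test. Recording at the end of the hospital stay would also miss a later emergency department visit, which the protocol itself counts as a consequence.

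At stake is a stated secondary hypothesis and any conclusion about economic benefit drawn from it.

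**Working it through.** **The plan's own figure.** The only sample size stated is for retention: 7% against 0.5%, two-sided 5% level, 80% power, 140 per group. Enumerating Fisher's exact test at 140 per group gives 80.3% power, which agrees. (The pooled normal approximation would ask for 133.) The plan gives no amount, standard deviation or detectable difference for charges, so no power for a difference in mean charges can be calculated.

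**Retention cases implied by the planning rates.**

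- Comparator: 140 × 0.07 = 9.8 cases.
- Sugammadex: 140 × 0.005 = 0.7 cases.
- Difference: 9.1 cases, or 0.07 − 0.005 = 0.065 per patient.

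**Effect on mean charges.** Let E be the extra charge per retention case and f the share of E that the statement captures. The documents give neither. The retention-driven mean difference is 0.065 × f × E per patient. E is assumed to lie between $2,000 and $10,000 for illustration.

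| f (assumed) | General | E = $2,000 | E = $10,000 |
|---|---|---|---|
| 1 | 0.065E | $130 | $650 |
| 0.5 | 0.0325E | $65 | $325 |
| 0 | 0 | $0 | $0 |

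The last row is a limiting case, not a forecast.

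**What the planned test can see.** The analysis section compares continuous variables by rank tests, not by means. Take the most favourable case: all charges are captured, every retention case is charged more than every other patient, and the groups differ in nothing else. The probability that a comparator patient's charge exceeds a Sugammadex patient's, counting ties in retention status as one half, is

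0.07 × 0.995 + 0.5 × [1 − (0.07 × 0.995 + 0.93 × 0.005)] = 0.06965 + 0.5 × 0.9257 = 0.5325.

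The null standard error is √[(2 × 140 + 1) / (12 × 140²)] = √(281 / 235,200) = 0.0346. The standardised effect is 0.0325 / 0.0346 = 0.94. Power is about Φ(0.94 − 1.96) + Φ(−0.94 − 1.96) = 0.154 + 0.002, or about 16%. A simulation of 4,000 runs with an assumed charge distribution gave 14.9%.

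**Terms side by side.** Objectives and Hypotheses speak of charges, Methods of cost to the patient, and the analysis section of hospital cost. The first three can be read as one quantity. Hospital cost cannot be obtained from the named source alone.

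**The case against.** The strongest reply is that a statement generated for a department may be one that the department receives, not one limited to its own fees. Such a report could list every hospital charge for its patients. This stands: the documents leave the contents undescribed and do not show that the source is wrong.

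A second reply is that charges accrued by patients and cost to the patient are naturally the same thing, and that the Study Summary is not a variable definition. This stands in part. It leaves hospital cost in the analysis section as the clear outlier, and the coverage question remains open.

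A third is that the rank test has only about 15% power for the retention-driven difference even with complete charges. This also stands. A null result could not be blamed on the billing report alone, and changing the source without adding an estimate of the mean difference would help little.

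A fourth is that length of stay, catheterisation and any admission are recorded directly. That is so, and it limits the damage, but it does not supply the charge comparison that the hypothesis promises.

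Two stronger readings are tempting. A reader might infer that the comparison would show no difference whatever the drug does. That requires f = 0, which the documents do not establish; the extra physician assessment listed in the Background could itself be departmental billing. A reader might also infer that the result would reflect payer mix, since insurance is not among the matching variables in Study Design/Methods. That requires the figure to be the patient's own share, which the Objectives and Hypotheses do not support.

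**Conclusion.** The point holds as a mismatch of definition and an unverified source. The plan hypothesises about charges, labels the analysed variable a cost, and names one billing report whose coverage it does not describe. If the report is partial, the retention-driven mean difference falls in proportion to the share captured. If it is complete, the naming problem remains and a conclusion about hospital cost still would not follow.

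The dollar figures rest on an assumed charge per case, and the captured share is unknown; only the 0.065 comes from the plan. The power figure assumes no other difference between cohorts. This is a secondary outcome, so the retention comparison is untouched, but the correction is cheap and worth making before charge data are extracted.

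**What to change.** In Study Design/Methods, take total billed charges (facility, anaesthesia, pharmacy and professional lines) from the full encounter account in Epic, or confirm in writing that the departmental statement already contains them. Use the same line categories in both cohorts and include retention-related return visits.

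Treat the reversal agent alike in both cohorts: exclude it from both, or add it to both at list charge. Otherwise Sugammadex, which the study budget pays for, may be absent from the treated patients' bills while the comparator's agent is present, and that would favour Sugammadex.

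In the analysis section, report the mean charge difference with a confidence interval alongside the rank test. Use one term, total billed charges, in the Study Summary, Objectives, Hypotheses, Study Design/Methods and Statistical Analysis sections, and limit the conclusion to charges. Conversion by cost-to-charge ratios is optional, and needed only if a statement about hospital cost is wanted.

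The price is a different report from the same billing system, aligned wording and a little more analysis. No patient contact is needed.
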